3.2.3. Protocol Deviations

Subjects with major protocol deviations will be summarized by prior ALKS 5461 exposure and overall along with supportive listings for each of the following categories:

- Did not meet the inclusion / exclusion criteria
- Received prohibited medications
- Lack of adherence with study medication, as defined by subjects taking less than 70% of the protocol specified amount of study medication
- Dosing error
- Other major protocol deviation

3.3. Demographics and Baseline Characteristics

For New Subjects only, demographic and baseline characteristics data (including MDD history) will be collected at screening visit. For Continuing Subjects and Lead-in Subjects, these data will be carried over from information recorded in the antecedent ALKS 5461 study in which they participated.

Demographics and baseline characteristics (age, gender, primary race, ethnicity, region (United States [US], non-US), duration of current MDE, ADT Class for current MDE, number of inadequate responses to ADT in the current MDE, lifetime number of MDEs, lifetime number of antidepressants, benzodiazepines (BDZ) use, opioid use, H1 antagonist use, height, weight, body mass index [BMI]) will be summarized by prior exposure to ALKS 5461, no prior exposure to ALKS 5461, and overall for the Safety Population. For no prior exposure to ALKS 5461, the group is divided further into 3 subgroups of De Novo, PLI Failures, and Placebo, as well as overall. Categories for missing data will be provided as necessary.

Baseline characteristics for efficacy measurments (MADRS-10 score, MADRS-6 score, HAM-A total score, CGI-S score and HAM-D total score) will be summarized by prior exposure to ALKS 5461, no prior exposure to ALKS 5461, and overall for the FAS Population. For no prior exposure to ALKS 5461, the group is divided further into three subgroups of De Novo, PLI Failures, and Placebo, as well as overall. The baseline for efficacy measurements is defined as the last non-missing value on or before the date of initiation of ALKS 5461 at any dose.

Medical and psychiatric history will be summarized using the number of observations and percentage of subjects reporting each category by prior ALKS 5461 exposure and overall for the Safety Population.

Demographic and baseline listings will be provided for all subjects.

3.5. Treatment Adherence Rate and Extent of Exposure

Treatment adherence to the daily dosing schedule of study drug is measured as the rate of actual compared to intended number of doses to be taken during the ALK5461-208 study. Percentage of treatment adherence will be calculated during 52-week treatment period for the Safety Population as follows:

 $\frac{\text{Total tablets taken}}{\text{Total tablets subject should have taken from the first dose date to the last dose date, inclusive}}$

Duration of exposure to study drug is defined as the number of days from the first dose date of study drug taken to the date of the last dose taken during the ALK5461-208 study, inclusive.

Treatment adherence and exposure of study drug will be summarized by prior ALKS 5461 exposure and overall for the Safety Population.

Treatment adherence will be summarized as a continuous measure using descriptive statistics (number of subjects, mean, SD, median, minimum, and maximum) and as a categorical measure using the number and percentage of subjects in each adherence rate category (rounded to the whole number): <70%; $\ge70\%$ to 80%; >80% to 90%; >90% to 100%; >100% to 110%; >110% to 119%; and $\ge120\%$.

The number of subjects exposed to study drug and the average days of treatment will be summarized as a continuous measure using descriptive statistics (number of subjects, mean, SD, median, minimum, and maximum).

The exposure to ADT will be summarized by ADT class (SSRI, SNRI, TCA, MAOI and other) and Preferred Term (ADT name) using descriptive statistics in a similar fashion. In addition, descriptive statistics of mean daily dose of ADT will be summarized by ADT class and Preferred Term.

The descending cumulative exposure of study drug will be categorized as ≥ 1 day, ≥ 1 month, ≥ 3 months, ≥ 6 months, ≥ 9 months and ≥ 12 months, and will be summarized as a categorical measure using the number and percentage of subjects in each category.

The definitions in Table 3 will be used to define cumulative exposure.

Table 3: Definitions to Define Study Drug Cumulative Exposure

	Definition	Programming Derivation
≥ 1 day	≥ 1 day	
≥ 1 month	≥ 23 days (3 weeks)	\geq (365.25/12)-7 days
\geq 3 months	\geq 84 days (12 weeks)	\geq [(365.25/12)x3]-7 days
≥ 6 months	≥ 169 days (24 weeks)	\geq [(365.25/12)x6]-14 days
≥ 9 months	≥ 260 days (37 weeks)	\geq [(365.25/12)x9]-14 days
≥ 12 months	≥ 351 days (50 weeks)	≥ 365.25 -14 days

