- Duration of TEAEs experienced by ≥5% of All Subjects by Preferred Term

• Incidence of TEAEs experienced by ≥5% of All Subjects by Preferred Term and Exposure Interval

A subject having the same AE (as determined by the coded MedDRA preferred term) more than once will be counted only once in the calculation of the number and percentage of subjects for that AE. Similarly, if a subject has more than one AE in a System Organ Class, the subject will be counted only once in the number of subjects with an AE for that System Organ Class. If a subject has the same AE on multiple occasions, the highest severity (severe > moderate > mild) recorded for the event will be presented in the AE by severity summary. Similarly, if a subject has the same AE on multiple occasions, the closest relationship (related > not related, where related includes definitely related, probably related, and possibly related; and not related includes probably not related and definitely not related) recorded for the event will be presented in the AE by relationship summary. If a subject has the same AE on multiple occasions, the first presentation will be used in the incidence table and the longest duration will be used in the duration table.

The number and percentage of subjects with TEAE during the ALK5461-208 study will be summarized by System Organ Class, Preferred Term, and duration of exposure since the first dose of the study drug in the ALK5461-208 study (1 day to <1 month, \geq 1 to <3 months, \geq 3 to <6 months, \geq 6 to <9 months, \geq 9 to <12 months, and \geq 12 months). For each exposure interval, the percentage will be calculated as the number of subjects with a new TEAE that started during the exposure interval, relative to the number of subjects exposed during the interval. Separate tables for prior ALKS 5461 exposure and overall will be provided.

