3.7.3. Adverse Events of Special Interest

Adverse events of special interest (AESIs) will be summarized by Preferred Term and by prior ALKS 5461 exposure and overall during treatment period for the Safety Population / Post-discontinuation Safety Population for any TEAEs or PDEAEs of special interest. The following summaries will be created for AESI:

- TEAEs associated with abuse potential
- TEAEs associated with dependence
- PDEAEs associated with withdrawal
- TEAEs associated with suicidal ideation and behavior
- TEAEs associated with hypomania / mania
- TEAEs associated with central nervous system (CNS) depression and sedation
- TEAEs associated with respiratory depression
- TEAEs associated with orthostasis / hypotension
- TEAEs associated with hypersensitivity

- TEAEs associated with slowing of ventricular repolarization
- TEAEs associated with hepatic effects
- TEAEs associated with sexual dysfunction

TEAEs associated with abuse potential will be presented by Adhoc System Organ Class and Preferred Term, where Adhoc System Organ Class is manually classified by Alkermes medical director as 3 categories: abuse behavior, euphoria related, and non-specific.

TEAEs associated with dependence will be presented for subjects with any exposure, ≥4 weeks exposure, and <4 weeks exposure, respectively.

PDEAEs associated with withdrawal will be presented for subjects with any exposure, ≥4 weeks exposure, and <4 weeks exposure, respectively. AESIs associated with withdrawal are PDEAEs that occur from >2 to 16 days post last dose as this is the period during which physiological opioid withdrawal presents by considering half-lives of both BUP and SAM.

Supportive AE listings will be provided for each special interest group. Narratives will be provided for clinically meaningful events within each AESI group.

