3.7.8. Clinical Opiate Withdrawal Scale (COWS) Scores

COWS will be administered only at EOT and post-discontinuation visits, so COWS will be analyzed for Post-discontinuation Safety Population. For Post-discontinuation Safety Population, baseline COWS is defined as EOT COWS assessment. Adequate COWS baseline is defined as EOT COWS assessment being performed within (\leq) 2 days of last dose of study drug.

Subjects will be included in the COWS analysis if they have an adequate EOT COWS and at least 1 post-EOT COWS in the post-discontinuation safety period. COWS will be summarized by:

- Analysis of all post-EOT COWS assessments
- Analysis of post-EOT COWS assessments that occurred from >2 to 16 days post last dose of study drug

Subjects with inadequate EOT COWS, i.e. EOT COWS assessment was performed more than (>) 2 days of last dose, will be included in a supportive listing.

Although opioid withdrawal might not be expected in individuals with less than 4 weeks of drug exposure, COWS will be presented in all subjects with adequate EOT COWS, and then COWS will be subset by duration of study drug exposure. Three COWS analyses will be presented for the subjects with adequate EOT COWS by the 3 exposure subgroups (any exposure, ≥4 weeks exposure, <4 weeks exposure):

- Total COWS scores (baseline and change from baseline, and days between last dose and assessment date) will be summarized by visit (baseline, post-discontinuation visits)
- Subject count and incidence will be provided by visit for each of the COWS total score categories indicated below:

No withdrawal: total score 0-4

Mild withdrawal: total score 5-12

Moderate withdrawal: total score 13-24

Moderately severe withdrawal: total score 25-36

- Severe withdrawal: total score >36

COWS category shift summary from baseline to post-baseline: the numerator is the
number of subjects in each post-discontinuation COWS category with non-missing
baseline COWS. If there are more than one post-discontinuation COWS, i.e. a subject
with an unscheduled visit, the highest value will be used. The denominator is the
number of subjects in each baseline COWS category.

Data listing of COWS scores at each visit will be provided. Narratives will be provided for any clinically meaningful COWS shifts.

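### The 4-week strata for dependence, withdrawal and COWS appear to use a 208-only exposure clock, so subjects who entered on drug and stopped early can be classed as having under 4 weeks of exposure

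*SAP*

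**What the plan says.** The general definition of exposure is in SAP 3.5: "Duration of exposure to study drug is defined as the number of days from the first dose date of study drug taken". The end point is tied to this study, with the count running "to the date of the last dose taken during the ALK5461-208 study, inclusive". SAP 3.7.2 makes the start point explicit for the adverse-event intervals, which use "duration of exposure since the first dose of the study drug in the ALK5461-208 study". SAP 3.1 adds that summaries are, in general, limited to data from this study.

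Three sets of tables are split into any exposure, at least 4 weeks, and under 4 weeks:

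- Dependence (SAP 3.7.3): "TEAEs associated with dependence will be presented for subjects with any exposure", then by the two 4-week groups.
- Withdrawal (SAP 3.7.3): "PDEAEs associated with withdrawal will be presented for subjects with any exposure", then by the same groups.
- COWS (SAP 3.7.8): "COWS will be subset by duration of study drug exposure".

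SAP 3.7.8 also gives the thinking behind the cut: "Although opioid withdrawal might not be expected in individuals with less than 4 weeks of drug exposure".

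Protocol 8.1, Table 1, shows that some Continuing Subjects enter on ALKS 5461 1/1 (from 207) or 2/2 (from 206, 207 or 210) and are not titrated. SAP 3.1 flags prior exposure as yes or no, whatever its length.

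**The concern.** The reason given for the cut is pharmacological: it concerns time on drug. The clock that the text supplies measures time in study 208. For new subjects, lead-in subjects and subjects who had only placebo, the two are the same. For a subject who entered on drug they differ by the whole antecedent dosing period.

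The sole objective is long-term safety and the product contains buprenorphine, so readers will look at withdrawal by length of exposure. They will take the under-4-week rows to mean short exposure. In the prior-exposed column those rows can include subjects with 28 or more days on drug, who are then absent from the stratum in which the SAP's rationale would place them. The overall column mixes them in. Showing the tables by prior exposure does not cure this, because that flag ignores duration.

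**Working it through.** **The plan's own figures.** The SAP gives no count for these strata. The nearest figures are the Table 3 exposure cut-offs. With a month of 365.25/12 = 30.4375 days:

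- 1 month: 30.4375 − 7 = 23.44
- 3 months: 91.3125 − 7 = 84.31
- 6 months: 182.625 − 14 = 168.63
- 9 months: 273.9375 − 14 = 259.94
- 12 months: 365.25 − 14 = 351.25

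Rounded, these match the stated 23, 84, 169, 260 and 351 days. None is 28 days, so Table 3 does not define the 4-week cut.

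**Which clock applies.** SAP 3.7.8 uses the term that 3.5 defines. SAP 3.7.3 uses the same strata and names no clock. SAP 3.1 and 3.7.2 both point to 208 dosing, and no section adds antecedent dosing days. The 208 clock is therefore the natural reading for COWS and an inference for dependence and withdrawal events.

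**Classification rule.** Take 4 weeks as 28 days. Let d be 208 dosing days and A the antecedent ALKS 5461 days. A is an assumption, since the documents give no antecedent treatment length. A subject is misplaced when d is 1 to 27 and A + d ≥ 28.

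Antecedent days needed, 28 − d:

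- d = 7: 21 days
- d = 14: 14 days
- d = 21: 7 days
- d = 27: 1 day

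The number of the 27 possible short durations that move is min(A, 27):

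| A (assumed) | Durations that move | Share of 27 |
|---|---|---|
| 7 | 7 | 26% |
| 14 | 14 | 52% |
| 21 | 21 | 78% |
| 27 or more | 27 | 100% |

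Example: with A = 35 and d = 15, the 208 clock gives 15 days and the cumulative clock 35 + 15 = 50. The figures are the same if an off-drug gap is bridged and its days are not counted.

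**Which cells are affected.**

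- No prior exposure: A = 0, so nothing changes.
- At least 4 weeks: d ≥ 28 implies A + d ≥ 28, so nobody is wrongly included. Some prior-exposed subjects are missing.
- Under 4 weeks, prior-exposed and overall: contaminated.
- Any exposure: unaffected.
- The 6- and 12-month exposure targets in SAP 2: the 208 clock is conservative.

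**Related baseline point.** SAP Table 2 takes the laboratory, vital-sign, ECG and C-SSRS baseline as the last value up to Visit 2, in line with Protocol 14.4. Protocol 8.1 lets antecedent end-of-treatment assessments stand in for Visit 2. For prior-exposed subjects this baseline can therefore be an on-drug or antecedent end-of-treatment value. That can include subjects from 205: Table 1 has them entering after a 1-week discontinuation, but Table 2 of the Protocol allows carry-forward within 10 days. COWS and post-discontinuation events are untouched, because their baselines are set around the end of treatment. By contrast, SAP 3.2.1 and 3.3 put the efficacy baseline for these subjects before their first antecedent dose.

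**The case against.** The strongest reply is that the SAP never states which clock the 4-week strata use. Where it plainly wants a 208 start, in 3.7.2, it says so. SAP 3.2.1 uses the term study drug for exposure in an earlier trial, and in 3.5 the reference to study 208 could grammatically attach to the last dose alone. The dataset and programming specifications and mock tables are separate documents and may settle the matter. The remark about 4 weeks is also a concessive clause explaining why all subjects are shown first, not a formal definition.

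The affected group is narrow too. A subject must have completed an antecedent treatment period, entered on active drug, and stopped within 27 days. For COWS the subject also needs an end-of-treatment assessment within 2 days of last dose and at least one later assessment.

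Much of this stands: the clock is partly inferred, and the tables are descriptive. But if the text allows two clocks that classify the same subject differently, the SAP still needs to choose, and the definition it gives in 3.5 leads to the wrong stratum.

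Two stronger readings are tempting. A reader might take 26%, 52% and 78% as misclassification rates. They are shares of possible durations, not of subjects, and they rest on an assumed A and no stopping distribution. A reader might also conclude that the Visit 2 safety baseline is an error that hides weight or QTcF effects. It is the baseline that the Protocol prescribes, the documents give no evidence of such shifts, and whether the antecedent reports show any earlier change cannot be seen here.

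**Conclusion.** The point holds in a limited form. On the SAP's exposure definition, prior-exposed subjects who entered on ALKS 5461 from 206, 207 or 210 and have 1 to 27 days of 208 dosing fall in the under-4-week stratum even when their total dosing reaches 28 days. If antecedent active dosing lasted 27 days or more, this applies to every such subject in that stratum. How many there are cannot be computed, because the documents give no prior-exposed head count, antecedent duration or early-stopping rate.

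The conclusion rests on reading 3.7.3 and 3.7.8 through 3.5 and on taking 4 weeks as 28 days. It does not reach the no-prior-exposure column or the any-exposure tables, and it does not mean that anyone is wrongly placed in the longer stratum. The safety-baseline matter is secondary and calls at most for a label and supportive tables. The efficacy baseline differs from Protocol 14.4 while SAP Section 5 records no changes; that is a documentation gap only.

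**What to change.** **Main change.** In SAP 3.7.3 and 3.7.8, define the 4-week strata for prior-exposed subjects on cumulative ALKS 5461 dosing days, antecedent plus 208. Bridge off-drug gaps up to the 10-day entry limit in Protocol 7.1.3, do not count the off-drug days, and apply the same rule to all four antecedent studies. Show the 208-only clock, or a shorter gap limit, as a sensitivity table.

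A 2-day limit would be a poor primary choice. It appears in the SAP for other purposes: the withdrawal window covers "PDEAEs that occur from >2 to 16 days post last dose", and an end-of-treatment COWS counts as adequate up to 2 days after last dose. Used to bridge exposure, it would send subjects with a gap of 3 to 10 days back to the under-4-week group.

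The cost is SAP wording, antecedent first- and last-dose dates (the efficacy baseline already needs the first), and a few extra descriptive tables. The strata will depend to some degree on the gap limit, hence the sensitivity table.

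**Optional.** Keep Visit 2 as the primary safety baseline. Footnote that for prior-exposed subjects it may be an on-drug or antecedent end-of-treatment value, including carried-forward values from 205 and including C-SSRS. Add supportive weight, laboratory PCS and shift, and QTcF-change tables using the last value before the first antecedent ALKS 5461 dose. This needs a new data merge, and the tables would cover antecedent completers only.

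**Documentation.** Record the efficacy-baseline departure in SAP Section 5.

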3.6. Efficacy Analysis

3.6.1. General Considerations

All efficacy analyses will be based on the FAS. Descriptive statistics will be summarized by prior ALKS 5461 exposure and overall based on observed data.

3.6.1.1. Pooling of Centers

No plan to pool study centers.

3.6.1.2. Multiple Comparisons/Multiplicity

Not applicable.

3.6.1.3. Examination of Subgroups

No subgroup analysis for efficacy is planned.

3.6.2. Efficacy Analysis

3.6.2.1. Montgomery-Asberg Depression Rating Scale (MADRS)

The MADRS measures the severity of depressive symptoms and consists of 10 items. The MADRS-10 is the sum of all 10 items and ranges from 0 to 60. The MADRS-6 is the sum of the following 6 items: item 1 reported sadness; item 2 apparent sadness; item 3 inner tension; item 7 lassitude; item 8 inability to feel; and item 9 pessimistic thoughts and ranges from 0 to 36. Section 6.2 describes the handling of MADRS-10 if any of the items of the MADRS is missing.

The following endpoints will be assessed:

- Change from baseline in MADRS-10 and MADRS-6 score
- Proportion of subjects demonstrating MADRS treatment response, defined as a ≥50% reduction in MADRS-10 from baseline
- Proportion of subjects achieving remission, defined as a MADRS-10 of \leq 10

Descriptive summary statistics of baseline MADRS-10 and MADRS-6 score and change from baseline at each visit including the last assessment during treatment period will be provided by prior ALKS 5461 exposure and overall based on observed data. In addition, the figures of MADRS-10 and MADRS-6 score (including standard error), mean change from baseline (including standard error) over time including the last assessment during treatment period will be provided by prior ALKS 5461 exposure and overall based on observed data.

The responder and remission endpoints are derived based on the observed MADRS-10. The number and percentage of subjects demonstrating MADRS-10 treatment response and remission by visit including the last assessment during treatment period will be provided based on FAS. The figures of MADRS-10 responder rate and MADRS-10 remission rate over time including the last assessment during treatment period will be provided by prior ALKS 5461 exposure and overall.

The individual MADRS item scores will not be summarized but will be included in the subject listing.

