7.1.2. New Subjects

In order to qualify for participation in this study, in addition to meeting the criteria for all subjects presented in Section 7.1.1, New Subjects must also meet all of the following criteria:

5. Be between 18 and 70 years of age, inclusive
6. Have a body mass index (BMI) 18.0 - 40.0 kg/m²
7. Have not been randomized in a prior study of ALKS 5461 within 2 years
8. Have a Diagnostic and Statistical Manual of Mental Disorders, Fourth Edition, Text Revision (DSM-IV-TR) MDD diagnosis at screening, as assessed and confirmed by the Mini International Neuropsychiatric Interview (MINI) administered by qualified site staff. The diagnosis of MDD must be considered by the investigator as the primary source of current distress and functional impairment
9. Have a current major depressive episode (MDE) lasting 8 weeks to 24 months
10. Have been treated with an adequate dose of an approved ADT during the current MDE for at least 8 weeks, with the same, adequate dose over the last 4 weeks, which is expected to remain stable throughout the study
11. Have an inadequate response to current ADT and up to 1 prior ADT during the current MDE. An inadequate response is defined as less than a 50% reduction in depressive symptom severity during a course of treatment at least 8 weeks in duration with an adequate dose of an approved ADT, as assessed on-site using the Massachusetts General Hospital Antidepressant Treatment Questionnaire (ATRQ)

(NOTE: If a subject had an adequate response to an ADT in the past, but now has relapsed on the same ADT at the same or lower dose and is experiencing a new MDE, this would not represent an adequate trial of an ADT for this new MDE)

12. Have a HAM-D total score of ≥ 14 at Visit 1 and ≥ 10 at Visit 2

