7.1.3. Continuing Subjects

In order to qualify for participation in this study, in addition to meeting the criteria for all subjects presented in [Section 7.1.1](#), Continuing Subjects must also meet the following criterion:

13. Have completed the treatment period of ALK5461-205, ALK5461-206, ALK5461-207, or ALK5461-210 within 10 days of Visit 2

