7.1.4. Lead-in Subjects

In order to qualify for participation in this study, in addition to meeting the criteria for all subjects presented in [Section 7.1.1](#), Lead-in Subjects must also meet all of the following criteria:

14. Have completed the prospective lead-in (PLI) of study ALK5461-205, ALK5461-206, or ALK5461-207 within the past 10 days; criteria for completion of the PLI includes 1) at least 8 weeks of ADT with at least 5 weeks at the minimally effective dose and 2) completion of Visits 1a through 1f

15. Have demonstrated a treatment response during the PLI of the antecedent study, but failed to achieve remission from MDD, as determined in an interactive voice or web response system (IxRS) using masked criteria

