3. DATA ANALYSIS

3.1. General Statistical Methodology

The safety and efficacy endpoints will be summarized by prior ALKS 5461 exposure: no prior exposure to ALKS 5461 and prior exposure to ALKS 5461, as well as overall.

Subjects with no prior exposure to ALKS 5461 come from three sources: De Novo (i.e., New Subjects), PLI Failures (i.e., antecedent study Prospective Lead-in Subjects Failures) and Placebo (i.e., those who did not receive any active treatment in an antecedent study).

Prior exposure to ALKS 5461 subjects include Continuing Subjects who received active treatment (doses ALKS 5461 0.5/0.5, ALKS 5461 1/1, or ALKS 5461 2/2) in an antecedent study. Subjects with prior exposure are designated as such independent of the duration of exposure in the antecedent trial.

In general, summary statistics (n, mean, standard deviation [SD], median, minimum, and maximum for continuous variables, and number and percentage of subjects in each category for categorical variables) based on observed data will be provided by prior ALKS 5461 exposure and overall. Measurements collected from unscheduled visits or repeated assessments will not be included in the by-visit summary tables or figures, but will be included in categorical outlier analyses of post-baseline values and subject listings.

In general, only data collected during the ALK5461-208 study will be summarized even though the baseline may come from an antecedent study.

Last assessment during treatment period, defined as the last non-missing value from scheduled post-baseline visit during the treatment period (i.e., from Visit 2 to Visit 14, inclusive), will be included in the by-visit summary tables for both efficacy and safety endpoints as appropriate.

Source data for the summary tables will be presented as subject data listings. Please refer to Section 6.1 on the handling of data collected at an early termination visit.

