3.2. Study Population

3.2.1. Definitions of Analysis Populations (Analysis Sets)

Safety Population consists of all subjects who receive at least 1 dose of study drug in the ALK5461-208 study.

An AE will be considered as a treatment emergent adverse event (TEAE) if it starts or worsens (if present at baseline) on or after the baseline during treatment period. An AE will be

considered as a post-discontinuation emergent adverse events (PDEAE) if it starts or worsens after the last dose date plus 1 day.

Post-discontinuation Safety Population consists of subjects in the Safety Population who have at least 1 post-discontinuation measurement. There will be two Post-discontinuation Safety Populations, one is used to analyze PDEAE, and the other is to analyze COWS, grouped by whether having had exposure to study drug in a prior controlled trial or had no prior exposure.

Post-discontinuation Safety Population for PDEAE consists of subjects who received at least 1 dose of study drug, and met one of the following criteria:

- Subjects who entered the Post-discontinuation Period and had a Post-discontinuation Visit
- Subjects who did not enter the Post-discontinuation Period, but had at least 1 PDEAE reported
- Subjects who died after either completing the treatment or having an Early Termination (ET) Visit

Post-discontinuation Safety Population for COWS consists of subjects who received at least 1 dose of study drug, had an adequate COWS baseline (defined as end of treatment [EOT] COWS assessment) and had at least 1 post-EOT COWS assessment, where an adequate EOT COWS is defined as having been performed within (≤) 2 days of last dose of study drug.

Full Analysis Set (FAS) consists of subjects in the Safety Population who have at least 1 post-baseline complete MADRS assessment.

The baseline for efficacy endpoints is defined as the last non-missing observation on or before the date of baseline visit (Visit 2) of ALKS 5461-208 study for subjects who are new to ALKS 5461 (ie, De Novo, PLI Failures, and Continuing Subjects who received placebo in antecedent study); or the last non-missing observation on or before the first dose of ALKS 5461 in antecedent study for Continuing Subjects who received any dose of ALKS 5461 (i.e., ALKS 5461 0.5/0.5, ALKS 5461 1/1, or ALKS 5461 2/2) in antecedent study.

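### Remission in the no-prior-exposure column counts placebo entrants already at MADRS-10 of 10 or below before their first ALKS 5461 dose, and outcomes are not split by entry route

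*SAP*

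**What the plan says.** **Endpoints.** SAP 3.6.2.1 defines remission by an absolute threshold: "Proportion of subjects achieving remission, defined as a MADRS-10 of" 10 or below. Response is relative: "Proportion of subjects demonstrating MADRS treatment response, defined as a ≥50% reduction in MADRS-10 from baseline". Both are tabulated and plotted by visit.

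**Population.** SAP 3.2.1 states that the full analysis set "consists of subjects in the Safety Population who have at least 1 post-baseline complete MADRS assessment". It sets no minimum starting score.

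**Entry criteria.** These differ by route:
- New Subjects (Protocol 7.1.2) must "Have a HAM-D total score of ≥ 14 at Visit 1 and ≥ 10 at Visit 2". That is a HAM-D floor, not a MADRS floor.
- Continuing Subjects (Protocol 7.1.3) must "Have completed the treatment period of ALK5461-205, ALK5461-206, ALK5461-207, or ALK5461-210 within 10 days of Visit 2". No severity threshold is attached.
- Lead-in Subjects (Protocol 7.1.4) must "Have demonstrated a treatment response during the PLI of the antecedent study, but failed to achieve remission from MDD", as judged by masked criteria.

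**Baseline.** Under SAP 3.2.1, subjects new to ALKS 5461, including Continuing Subjects who took placebo, take the last value on or before Visit 2. Subjects with prior exposure take the last value on or before their first ALKS 5461 dose in the antecedent study.

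**Reporting groups.** SAP 3.1 says that subjects with no prior exposure "come from three sources: De Novo (i.e., New Subjects), PLI Failures" and Placebo. SAP 3.2.2 and 3.3 show disposition, demographics and baseline efficacy scores for these three sources separately. SAP 3.6.1 shows efficacy outcomes only by prior exposure and overall, and SAP 3.6.1.3 plans no efficacy subgroups.

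**The concern.** The word *achieving* implies a change of state. A placebo subject who completes the antecedent trial, enters at a MADRS-10 of 8 and stays at 8 has not changed. The plan nevertheless counts that subject as achieving remission at every visit, and as a non-responder in the response table.

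The study has no comparator, so the pre-dose state is the only reference for reading a remission curve. The no-prior-exposure column is where a reader will look for what happens after ALKS 5461 is started. If that curve does not begin at zero and the plan does not specify a Visit 2 remission percentage, part of what it shows came before the drug.

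The second issue is the mix within the column. Protocol 8.1 and SAP 1.2 describe the study population as subjects with one or two inadequate responses to an antidepressant. Lead-in Subjects had responded to theirs in the lead-in. Pooling them with New Subjects and placebo entrants gives one rate over groups that differ in history and probably in prognosis.

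**Working it through.** The plan states no remission or response rate, so there is no planned figure to reproduce. The check has three parts.

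**1. Who can meet each endpoint without changing?** From a starting score B, remission needs a drop of max(0, B − 10) and response needs a drop of B/2.

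| B | Drop for remission | Drop for response |
|---|---|---|
| 8 | 0 | 4 |
| 10 | 0 | 5 |
| 12 | 2 | 6 |
| 15 | 5 | 7.5 |
| 20 | 10 | 10 |
| 30 | 20 | 15 |

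At 10 or below, remission needs no improvement at all, whereas response always needs a halving. Below 20, remission is the easier endpoint; above 20, response is. A low Visit 2 score therefore helps a subject count as remitted but does not make the subject a responder.

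**2. Effect on the remission percentage.** Let p0 be the share of the column at 10 or below at Visit 2, s the share of those still there at a later visit, and r the remission rate among those who started above 10.

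- Counted remission = p0 × s + (1 − p0) × r.
- Excess over r = p0 × (s − r).

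The documents give none of these values. All of the following are assumptions: placebo entrants 20–40% of the column, 10–30% of them already at 10 or below, r = 30%, s = 80%.

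- Low end: p0 = 0.20 × 0.10 = 2%; counted = 0.02 × 0.80 + 0.98 × 0.30 = 31.0%.
- High end: p0 = 0.40 × 0.30 = 12%; counted = 0.12 × 0.80 + 0.88 × 0.30 = 36.0%.

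Other assumed values, with s = 60–80%:

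| p0 | Counted if r = 20% | Counted if r = 40% |
|---|---|---|
| 0% | 20% | 40% |
| 5% | 22–23% | 41–42% |
| 10% | 24–26% | 42–44% |
| 20% | 28–32% | 44–48% |

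The excess is upward whenever s exceeds r, and it vanishes when p0 = 0. In the overall column it is multiplied by the no-prior-exposure share of subjects, which the documents do not give.

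**3. Effect of pooling Lead-in Subjects.** Pooled rate = w × a + (1 − w) × b, where w is the Lead-in share, a their rate and b the rate in the others. All values are assumed.

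| w | Remission (b = 30%, a = 40–60%) | Response (b = 40%, a = 25–55%) |
|---|---|---|
| 10% | 31–33% | 38.5–41.5% |
| 20% | 32–36% | 37–43% |
| 30% | 33–39% | 35.5–44.5% |

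For response the pooled rate may move either way. Lead-in Subjects start from a Visit 2 score that already contains their antidepressant gain, and nothing in the documents says whether a further halving is more or less likely for them.

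**The case against.** The sole objective is long-term safety and tolerability (Protocol 6, SAP 1.1). Efficacy is exploratory and descriptive (Protocol 11 and 14.5), with no test or threshold that a few percentage points could cross. Percentage in remission by visit can be read as point prevalence, a reasonable summary for a 52-week open-label study. Baseline MADRS-10 is tabulated for the three sources, mean change is reported, and source data are listed by subject. Protocol 7.1.1 also requires that the investigator see potential benefit for every entrant, which may keep some well subjects out.

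Much of this stands, and it limits the priority. It does not remove the point. The endpoint is worded as attainment, not prevalence. The baseline table gives n, mean, SD, median, minimum and maximum, so it can show that someone was at 10 or below but not how many. The investigator's judgement is not a severity threshold.

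A reader might also infer more than the documents support:
- *That response is misattributed too.* It is not. In this column response is measured from Visit 2, so improvement before that visit is already in the baseline.
- *That every subject at 10 or below at Visit 2 was so before any ALKS 5461.* Prior-exposure subjects had already taken the drug, and their baseline precedes that first dose. Counting them follows the SAP's own definition.
- *That Lead-in Subjects are a source of pre-dose remitters.* They had to be non-remitted, although the scale and cutoff are masked. Their issue is pooling.
- *That the PLI Failures label distorts an analysis.* SAP 3.2.2 equates it with Lead-in Subjects, so renaming would be cosmetic.

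**Conclusion.** The point holds for remission in the no-prior-exposure column and, diluted, in the overall column. The clear route is the Continuing Subject who took placebo. A New Subject with a HAM-D of 10 or more could also have a MADRS-10 of 10 or below, but the documents do not show how often. Separately, remission and response in this column are averages over unlike entry routes and cannot be read by source from the planned summary tables. For response, that is heterogeneity of unknown direction.

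The size cannot be derived from the documents. Under the main assumed values a true 30% appears as 31–36%, an excess of 1 to 6 percentage points. It is zero if nobody enters at 10 or below. Because efficacy is exploratory and uncontrolled, priority is low to moderate. The case for acting is that the correction is cheap and removes a likely upward bias from a rate whose only reference is the pre-dose state.

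**What to change.** In SAP 3.6.2.1, for the no-prior-exposure group:

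1. Report the percentage with MADRS-10 of 10 or below at Visit 2.
2. Report remission by visit among subjects whose Visit 2 baseline MADRS-10 is above 10.
3. Report maintained remission separately, among those at 10 or below at Visit 2.
4. Show remission and response for the De Novo, Lead-in and Placebo subgroups already defined in SAP 3.2.2 and 3.3, and amend SAP 3.6.1.3 to match.

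For prior-exposure subjects, keep the baseline before the first ALKS 5461 dose and state that remission is cumulative from the antecedent study. Label the overall column as the percentage at 10 or below, since it mixes the two reference points.

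No new data are needed. The cost is SAP wording, extra table columns, smaller denominators within each source, and probably a slightly lower reported remission rate.
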